### 4.2 Study Design

This study will be an interventional two-arm prospective cohort study. Both arms (PAD and CAD participants) will undergo the same standard 6 month out-patient cardiac rehabilitation program.

### 4.3 A description of the measures taken to minimize/avoid bias

The University of Health Network policy requires that all patients be aware of any medical treatment they are receiving and provide informed consent. As a result, it is not possible for patients to be blinded to which treatment they are receiving.

To avoid bias for the ankle brachial index measurement, the order in which blood pressure is measured on each limb will be randomized.

### 4.4 A description of the trial treatment(s)/ intervention

The standard 6-month out-patient cardiac rehabilitation program consists of weekly 1.5 hour visits to the TRI Rumsey Centre. After determining baseline VO2peak from the exercise stress test, an individualized walking exercise prescription will be developed by a cardiac rehabilitation supervisor which corresponds to approximately 60 to 80% of the participant's VO2peak. Participants will be invited to walk around the track and attend education sessions at the same time every week for six months. Patients will be encouraged to gradually increase their exercise time walking speed. Patients will be encouraged to exercise five times a week with four sessions occurring outside of the cardiac rehabilitation program.

### 4.5 The expected duration of subject participation

Participants will be part of the program for 6 months, as per standard care procedures.

### 4.6 The expected frequency and duration of study visits (anticipated time commitment) for study participants

There will be six study visits in total which coincide with standard care visits as well as the weekly visits to the cardiac rehabilitation program. Participants will not be required to make any additional visits outside of the standard cardiac rehabilitation program.

## Comparing the efficacy of cardiac rehabilitation for patients with peripheral artery disease to patients with coronary artery disease/Protocol #03

The first visit will take approximately 60 minutes and is consistent with standard care at the TRI Rumsey Centre cardiac rehabilitation program. A cardiac rehabilitation staff member will measure anthropometrics, blood pressure and will review medical history (e.g. smoking status, diabetes status, medications, current exercise regimen). The patient will also meet with a physician to review any concerns with starting the cardiac rehabilitation program. The patient will also be introduced to the study investigator if the patient expresses an interest in participating in the research study. All patients are given a blood work requisition to be completed at their local medical laboratory and if patients choose to consent to participating in the study, they will be given two questionnaires (WIQ and SF-36) to be completed for their next visit (approximately 15 minutes to complete both questionnaires).

The second visit is also consistent with standard care procedures and involves an exercise stress test with cardiac rehabilitation staff members. The exercise test will take approximately 60 minutes including preparation time, exercise time and time for questions. For the exercise stress test, patients will walk on a treadmill or pedal on a bicycle while having their breathing and blood pressure analyzed to measure VO2peak. Patients will also be attached to a 12-lead electrocardiogram to non-invasively measure activity of the heart.

The third visit will take approximately 30 minutes and will occur before the first cardiac rehabilitation class. While lying down in a private examination room, participants will have their blood pressure measured with an automated machine twice on the right arm, left arm, right ankle and left ankle in a random order. This will allow for calculation of the ankle brachial index for characteristic purposes.

The fourth visit will take approximately 60 minutes with 15 minutes occurring before class and 45 minutes during the exercise portion of the cardiac rehabilitation class. Prior to class, participants will participate in a 6-minute walk test to measure functional capacity. This will consist of participants walking as far as they can in 6 minutes at their own pace. During the 45 minute exercise component of the cardiac rehabilitation class, participants will have a chest strap placed underneath their clothing at the xiphoid-level to measure exercising heart rate.

The fifth visit will take approximately 60 minutes and will be structured exactly like the fourth study visit. Participants will be asked to participate in a 6-minute walk test 15 minutes prior to class and will have a heart rate monitor chest strap attached underneath their clothing while participating in the exercise portion of the cardiac rehabilitation class. Participants will also be given two questionnaires (WIQ and SF-36) to complete for their next visit (approximately 15 minutes).

The sixth and final visit at the 6 month mark of the program will take approximately 30 minutes. Participants will participate in the 6 minute walk test and will be given two questionnaires (WIQ and SF-36) to complete. During class, participants will have a heart rate monitor chest strap attached underneath their clothing.

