## Comparing the efficacy of cardiac rehabilitation for patients with peripheral artery disease to patients with coronary artery disease/Protocol #03

Hospital to the TRI cardiac rehabilitation program. Upon the initial assessment at TRI, PAD patients will be informed about participating in the proposed study by the principal investigator. CAD patients who have attended an initial assessment and have consented to chart review will have their patient file reviewed to determine if the patient is an appropriate match to a PAD patient based on sex, age, presence of diabetes, and assigned cardiac rehabilitation supervisor. One of the study investigators will then inform the patient during their second assessment at TRI about the study and invite the patient to participate in the study.

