## **4.0 Study Design**

### **4.1 Primary and secondary endpoints**

Patients will undergo a baseline assessment with a laboratory technician involving a standard battery of measurements and questionnaires for characteristic purposes including anthropometrics, resting blood pressure, resting heart rate, smoking status, diabetes status, current exercise regimen, and current medications. During this assessment, clinicians will review previous and ongoing medical treatment (i.e. surgical procedures, next physician visit, ankle-brachial index measurement), presence of angina, and conduct resting 12-lead electrocardiograms. This will be followed by a medical assessment by a physician to further review medical history and safety precautions for exercise. Patients will be sent home with a walking impairment questionnaire (WIQ) (McDermott et al., 1998) and a quality of life (QOL) questionnaire (SF-36) (Brazier et al., 1992) to be submitted at their next visit. A requisition for blood work will also be given to patients to be completed prior to their second visit to determine HbA1c and total cholesterol levels.

During the second visit patients will undergo a maximal cardiopulmonary exercise test to determine cardiorespiratory fitness as measured by VO2peak and will also have an exercising 12-lead electrocardiogram. The cardiopulmonary exercise test will consist of a Bruce or modified Bruce treadmill protocol (Noonan and Dean, 2000).

After determining baseline VO2peak, an individualized walking exercise prescription will be developed by a cardiac rehabilitation supervisor which corresponds to approximately 60 to 80% of VO2peak. Patients will be invited to attend weekly 90-minute supervised exercise and education sessions at the same time every week for six months, as per standard care procedures. Patients will be encouraged to gradually increase their exercise time per session as well as frequency of sessions per week.

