Clinicians at TRI will record distance walked, rest periods, exercising heart rate (as palpated by the radial pulse), ratings of perceived exertion and ratings of pain severity on a scale of 0 (no pain) to 10 (worst imaginable pain) (Hawker, Mian, Kendzerska, & French, 2011) for each exercise session at TRI. Patients will self-record their other exercise sessions on a weekly basis using standard exercise diaries. Frequency, time, type, exercising heart rate and rating of perceived exertion will be recorded for each exercise session outside of TRI. Patients will wear a non-invasive heart rate monitor (Polar) while walking at the 2nd week, 3rd month and 6th month mark of the program to help determine acute responses to aerobic exercise. Average exercising heart rate will be measured and recorded. VO2peak, 6MWT, QOL (SF-36), and walking impairment (WIQ) will be re-assessed at the 3 month and 6 month mark of the program.

Training volume will be quantified for each group for the prescribed and actual exercise load. For aerobic exercise, training will be calculated as the product of intensity in heart rate reserve, duration, and frequency for both the prescribed and actual exercise. For resistance exercise, training will be calculated as the product of weight, numbers of sets, and number of repetitions for each exercise for both prescribed and actual exercise.

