## Comparing the efficacy of cardiac rehabilitation for patients with peripheral artery disease to patients with coronary artery disease/Protocol #03

The primary endpoints of interest include change in VO2peak from month 6 to baseline, change in 6 minute walk test distance from month 6 to baseline, as well as change in walking impairment and quality of life as assessed through questionnaires from month 6 to baseline.

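### As written, CAD patients alone have no scheduled baseline WIQ/SF-36, the exercise-test mode is stated in two ways, and no 6MWT is listed before the first class

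*Combined protocol and SAP*

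**What the plan says.** Section 4.1 defines the endpoints as changes to month 6 in VO2peak, 6MWT, walking impairment and quality of life; for the walk test it is "change in 6 minute walk test distance from month 6 to baseline". Each therefore needs a baseline value.

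**Questionnaires.** Section 4.1 says of the first assessment: "Patients will be sent home with a walking impairment questionnaire", together with the SF-36, for return at the next visit. No consent condition is attached. Section 4.6 attaches one: at visit 1, if patients consent to the study, "they will be given two questionnaires (WIQ and SF-36) to be completed for their next visit". On recruitment, Section 2.4 says "CAD patients who have attended an initial assessment and have consented to chart review will have their patient file reviewed" to find a match for a PAD patient, and that these patients are told of the study at their second assessment. Sections 11.1 and 11.1.1 agree, and the latter has the exercise-test staff raise it. Section 11.1 requires written consent before participation.

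**Exercise-test mode.** Section 4.1 specifies a Bruce or modified Bruce treadmill protocol, and Section 7.0 also describes VO2peak as a treadmill measure. Section 4.6, visit 2, allows a treadmill or a bicycle.

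**Walk test.** Section 4.6 says "The third visit will take approximately 30 minutes and will occur before the first cardiac rehabilitation class" and lists only arm and ankle blood pressures for it. At visit 4, "Prior to class, participants will participate in a 6-minute walk test to measure functional capacity", and a chest strap is worn in the class that follows. Visit 4 has no date. Section 4.1 has the heart rate monitor worn "while walking at the 2 nd week, 3 rd month and 6 th month mark of the program".

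**The concern.** A change score is only as good as its baseline, and here the gaps do not fall equally on the two groups.

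The questionnaire gap affects CAD patients only. Section 3.2 predicts larger WIQ and quality-of-life gains in PAD. If CAD patients complete the forms late, after training has begun to help, their change is understated and the comparison leans towards that prediction. If they never complete a baseline form, no change can be calculated. Section 8.3 carries the loss further, because a participant with a missing variable leaves the main analysis altogether, VO2peak included.

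The test-mode conflict concerns the variable that Section 3.1.1 names as primary. Nothing requires a patient to repeat the baseline mode at month 6. If the modes read differently, a switch would be counted as a training response.

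The walk test set the sample size in Section 8.2, so its baseline should be identifiable. If the first test comes after classes have begun, some of the gain is already inside the baseline.

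**Working it through.** **1. Questionnaires: the passages side by side**

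| Step | PAD | CAD |
|---|---|---|
| First told of the study | Initial assessment (2.4, 11.1) | Second assessment, the exercise test (2.4, 11.1, 11.1.1) |
| Earliest consent | Visit 1 | Visit 2 |
| Hand-out at visit 1, on consent (4.6) | Possible | Not possible |
| Hand-out at visits 2, 3 or 4 (4.6) | None listed | None listed |
| Next listed hand-out (4.6) | Visit 5 | Visit 5 |

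Read alone, the unconditional sentence in Section 4.1 would reach every patient at the first assessment. It cannot be applied to CAD patients, because at that point they have not been matched, told of the study or asked for the consent that Section 11.1 requires first. A usable baseline is still feasible: visit 3 comes after visit 2 and before the first class.

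Under Section 8.3, a CAD patient without a baseline form leaves the main analysis. Partial data stay only in the intention-to-treat analysis, where VO2peak change could be used but WIQ and SF-36 change could not be formed.

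**2. Test mode**

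Sections 4.1 and 7.0 describe a treadmill; Section 4.6 describes a treadmill or a bicycle. Both 4.1 and 4.6 refer to the same visit-2 test, so they cannot both stand. Section 4.1 schedules re-tests at months 3 and 6 without saying that the mode is kept. The documents give no switching rate and no difference between modes, so there is nothing to calculate.

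**3. Walk test**

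*The plan's own figure.* Section 8.2 gives 23 per group for a 10 m difference, alpha 5% and power 0.8. Taking the only 6MWT SD given there (12 m) and a two-sided test:

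n = 2 × 12² × (1.960 + 0.842)² / 10² = 288 × 7.85 / 100 = 22.6, so 23. It reproduces.

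*Date of visit 4.* Section 4.6 has the chest strap at visits 4, 5 and 6. Section 4.1 has the monitor at week 2, month 3 and month 6. Matching in order puts visit 4 at about week 2. This is an inference.

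*Training before it.* Section 4.4 says "Patients will be encouraged to exercise five times a week with four sessions occurring outside of the cardiac rehabilitation program". Before a week-2 class that is at most one class plus four other sessions:

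- 5 / (5 × 26) = 5/130 = 1/26 of the programme;
- 2/26 if the test falls at the end of week 2.

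Section 4.1 has patients build up weekly frequency gradually, so the true share of sessions is probably lower.

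*Shift in the group difference, assuming gain in proportion to that share:*

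- Using the gains cited in 8.2 (34.9 m PAD, 29.6 m CAD): 5.3 × 1/26 = 0.2 m; 5.3 × 2/26 = 0.4 m.
- Using the planned 10 m: 10 × 1/26 = 0.4 m; 10 × 2/26 = 0.8 m.
- If early gains are equal in the two groups: 0 m.

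The 34.9 m is against untrained controls and the 29.6 m is within group, so the first line is only a rough projection.

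**The case against.** The best defence is that the intention is clear and the gaps are in drafting. Section 4.1 plainly means every patient to have a baseline questionnaire, staff could give it to CAD patients at visit 2, and there is time to collect it before the first class. That stands as to intention. It does not remove the defect, because Section 4.6 lists no such hand-out and staff who follow it would miss one group only.

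It is also fair to say that the loss from the VO2peak analysis comes from the deletion rule in Section 8.3, which would act on any missing variable, and that the intention-to-treat analysis keeps partial data. Both are true. They limit the consequence without closing the gap.

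On test mode, the bicycle appears only in a section on time commitment, while two other sections point to the treadmill. That may show which text is the stray one, but it is for the authors to settle.

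A reader might infer more than the documents support:

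- *That CAD patients will have no baseline questionnaires.* The text shows only that none is scheduled; how many would lack one is unknown.
- *That VO2peak is biased by a change of mode.* No passage says that patients switch or that the modes differ.
- *That a week-2 walk test damages the group comparison or its power.* The date is inferred, the shift is small, and it vanishes if early gains are equal. Baseline VO2peak is measured at visit 2, before training, and is untouched.
- *That there is no follow-up VO2peak because Section 4.6 does not list it.* Section 4.1 schedules it at months 3 and 6.

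**Conclusion.** The point holds as a set of inconsistencies that should be fixed before enrolment, in this order of weight.

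1. As the schedule is written, CAD patients alone have no scheduled baseline for WIQ and quality-of-life change. This follows directly from the text. Its size depends on how many CAD patients would miss or delay the forms, which the documents do not give.
2. Sections 4.1 and 4.6 contradict each other on how the primary variable is measured, and nothing keeps the mode constant within a patient. This too is certain from the text, and its effect cannot be sized.
3. No 6MWT is listed before the first class. This is the lesser point. If visit 4 is at week 2 and gains are linear, each group's change is slightly understated and the group difference moves by about 0.2 to 0.8 m against the planned 10 m, or by nothing if early gains are equal. A faster early gain would enlarge this; the gradual build-up of sessions would reduce it.

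**What to change.** - **Questionnaires (Sections 4.1 and 4.6).** Give CAD patients the WIQ and SF-36 at visit 2, after consent, and collect them at visit 3 before the first class. Sections 2.4 and 11.1.1 already fit this and need no change.
- **Test mode (Sections 4.1, 4.6 and 7.0).** Reconcile the passages. State that each patient is re-tested at months 3 and 6 with the same mode and protocol as at baseline, and flag any switch for a sensitivity analysis.
- **Walk test (Section 4.6).** Move the first 6MWT to visit 3, after the resting pressures and before the first class. Rewrite visit 5, which is now described as a copy of visit 4, so that its own walk test is kept. If the test cannot be moved, date visit 4 and define the 6MWT endpoint as change from that visit.

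The cost is protocol wording. Visit 3 becomes about 15 minutes longer, offset by the 15 minutes before class that are freed at visit 4. No measurement or visit is added, so the commitment in Section 4.6 to no extra visits still holds. A baseline missed before training cannot be recovered later.

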#### 3.1.1 Primary objective

The primary objective of this proposed study is to compare the magnitude of the responses to a 6-month cardiac rehabilitation program for patients with PAD in contrast to patients with CAD. The primary variable of interest will be peak oxygen consumption ( $VO_2\text{peak}$ ) with a secondary variable of interest being functional capacity, as measured by the 6-minute walk test. Tertiary variables of interest will include walking impairment, as measured by the Walking Impairment Questionnaire, and quality of life, as measured by the Short Form-36 health survey (SF-36).

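### Sections 4.1 and 4.6 contradict each other on the month-6 VO2peak: it is planned in the first, but the six-visit schedule in the second holds an exercise test only at baseline.

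*Combined protocol and SAP*

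**What the plan says.** Section 3.1.1 sets the priority: "The primary variable of interest will be peak oxygen consumption". Section 4.1 lists VO2peak with the walk test and the two questionnaires as measures that "will be re-assessed at the 3 month and 6 month mark of the program", and closes by making the change to month 6 an endpoint. Section 8.1 analyses each outcome with a time factor of two levels, baseline and end.

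Section 4.6 gives the only visit-by-visit schedule. It opens: "There will be six study visits in total which coincide with standard care visits as well as the weekly visits to the cardiac rehabilitation program". It adds: "Participants will not be required to make any additional visits outside of the standard cardiac rehabilitation program". The exercise stress test appears at visit 2, where its length is given: "The exercise test will take approximately 60 minutes including preparation time, exercise time and time for questions". Visits 3 to 6 contain no exercise test. On the last of them the text says: "The sixth and final visit at the 6 month mark of the program will take approximately 30 minutes".

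The Protocol Summary describes the cardiopulmonary exercise test only among the assessments made before the program begins. Section 4.8 includes VO2peak in the data to be collected but attaches no time point to it.

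**The concern.** Someone running the study from section 4.6 would test each participant once, before the program, and would finish at month 6 with a walk test, two questionnaires and heart rate monitoring. The baseline VO2peak would then have no follow-up value to be compared with.

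This matters because the trial's lead question is whether VO2peak improves more in one disease group than in the other. Section 8.3 widens the effect: a participant with a missing variable is dropped in full from the main analysis. Read literally, a missing month-6 VO2peak also removes that person's walk test, WIQ and SF-36 results from it.

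**Working it through.** No sample-size or power figure is at issue. The check sets the assessments in 4.1 against those in 4.6 and compares the stated times.

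**Step 1. Content of the six visits (section 4.6).**

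| Visit | Stated length | Assessments | Exercise test? |
|---|---|---|---|
| 1 | about 60 min | intake, physician review, questionnaires handed out | no |
| 2 | about 60 min | exercise stress test | **yes (baseline)** |
| 3 | about 30 min | ankle brachial index | no |
| 4 | about 60 min | walk test, heart rate strap in class | no |
| 5 | about 60 min | as visit 4, questionnaires handed out | no |
| 6 | about 30 min | walk test, questionnaires, heart rate strap in class | no |

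**Step 2. Count the tests.** Section 4.1 requires baseline + month 3 + month 6 = 3. Section 4.6 contains 1. The shortfall is 3 − 1 = 2. The endpoint and the main analysis of variance use only baseline and month 6, so just one of the two missing tests, the month-6 one, affects the primary comparison.

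**Step 3. Could the test be read into an existing visit?**

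- Visit 6: about 60 minutes needed, about 30 stated. It does not fit even if the visit held nothing else.
- Visit 5: built like visit 4, with 15 minutes before class and 45 minutes of class. 15 + 45 = 60, so the stated time is already used. Section 4.6 does not label visit 5 as month 3; that timing is inferred from the heart rate monitor schedule in 4.1 (week 2, month 3, month 6).
- After visit 6: the schedule calls it the final visit, and section 4.5 ends participation at 6 months.

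**Step 4. Could standard care supply it?** The Protocol Summary places the test before the program starts. Section 4.6 describes the baseline test as standard care and still counts it as visit 2, so being standard care is not by itself a reason for a test to be left off the list. No section describes a standard-care test at month 3 or month 6.

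**Step 5. Effect on the analysis.** Without a month-6 value, the end level of the time factor in section 8.1 is empty for VO2peak. By section 8.3, the participant leaves the main analysis and the available data go to the intention-to-treat analysis. That keeps the other outcomes in use but does not create a follow-up VO2peak. For scale, section 8.2 enrols 28 per group so that 23 remain, a margin of 28 − 23 = 5 per group for losses of every kind.

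**The case against.** The strongest defence is that the measurement is plainly planned. Section 4.1 gives the time points, and section 8.1 analyses a follow-up value. Section 4.6 is headed as a statement of visit frequency and time commitment, so it need not list every assessment. A routine source is also plausible: rehabilitation staff run the exercise test as standard care, and section 4.8 lists VO2peak directly after describing consented chart review. If a routine month-6 test exists, one sentence naming it would close the gap.

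Much of this stands. It shows that the problem is a conflict between sections and not a missing intention. It does not remove the conflict, because no section says that a routine follow-up test exists and the one standard-care test that is described does appear in the schedule.

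Three stronger readings are tempting, and the documents do not support them.

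- A reader might infer that none of the 56 participants (28 × 2) will have a month-6 VO2peak. That follows only if 4.6 overrides 4.1, and nothing says that it does.
- A reader might add 15 + 45 + 15 = 75 minutes of content for visit 6 and call the visit impossible even without a test. That sum counts class time and assumes that the questionnaires are completed on site. Leaving class out, 15 + 15 = 30, which is the stated length. Visits 4 and 5 do count class time, so the counting convention is uneven, but 75 minutes is not established.
- A reader might treat the absent month-3 test as damage to the primary endpoint. Neither the endpoint nor the main analysis uses month 3.

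**Conclusion.** Wrong as written, and worth correcting. Section 4.1 calls for three exercise tests and section 4.6 provides one. The omission that matters is the month-6 test: about 60 minutes are needed, the final visit has about 30, and no other source is named.

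The consequence is conditional. If a site follows 4.6 literally, the follow-up VO2peak is not collected and the main analysis of the primary variable cannot be done. If a site follows 4.1, or if a routine test exists that the documents do not mention, the value will be there. The documents do not allow a count of how many participants would be affected. Nor would everything be lost: section 4.1 also lists the walk test, walking impairment and quality of life among its endpoints, section 4.6 schedules them at month 6, and section 8.3 keeps partial data in the intention-to-treat analysis.

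**What to change.** Reconcile 4.1 with 4.6. State in 4.6 which visit provides the month-6 VO2peak or, if it comes from a standard-care test, name that test and say that its result is retrieved by chart review. Do the same for the month-3 value that 4.1 promises. Then correct the visit count and the stated time to match. If the tests are study visits, the time commitment rises by about 60 minutes each, or 2 × 60 = 120 minutes per participant. If they are routine tests, a sentence naming the source may be enough.

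The cost is an amendment to wording, submitted to the Research Ethics Board as section 11.3 requires. No new procedure is added, because 4.1 already plans both tests. A time window for the follow-up test and its order relative to the walk test would be useful but are optional; the conflict can be resolved without them.
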